8.6. Study Schedule

Observations and tests for evaluating safety and efficacy will be performed following the schedule below (Table 11).

Table 11 Schedule of observations and tests

		Before treatment	During protocol treatment				At termination	After discontinuation of the protocol treatment
Cycle	1				Right before the start of each cycle			
Week	1		2	3	4			
Patient characteristics* ¹		○						
Signs and symptoms, and blood pressure		○	○	○	○	○	○	
Body weight		○	○	○	○	○	○	
Chest X-ray		○						
Electrocardiography		○						
Lesion measurements* ²		○			○	○	○	○
Clinical assessments	Hematology* ³	○	○	○	○	○	○	○
	Blood biochemistry* ⁴	○	○	○	○	○	○	○
	Coagulation* ⁵	○	○	○	○	○	○	○
	Tumor markers* ⁶	○			○	○	○	
	Hepatitis virus	○						
Adherence to study treatment			○	○	○	○	○	
CRFs	Enrollment Eligibility Form	○						
	Patient Characteristics Report	○						
	Progress Report					○		
	Antitumor Effect Report					○	(○)	
	Treatment Completion Report						○	
	Treatment Suspension (Considering Discontinuation) Report						○	
	Follow-up Form							○

*1 Patient characteristics: Sex, height, pathological diagnosis, treatment history, disease stage, ECOG-PS, allergies, concomitant diseases

*2 Imaging: Lesions will be imaged by dynamic CT or dynamic MRI 4 weeks (± 1 week) after the start of treatment and every 8 weeks thereafter until progression is confirmed.

*3 Hematology parameters: Hemoglobin, white blood cell count, neutrophil count, red blood cell count, platelet count

*4 Blood biochemistry: AST, ALT, total bilirubin, direct bilirubin, ALP, γ -GTP, albumin, creatinine,

Na, K, Cl, amylase, lipase, blood glucose

*5 Coagulation profile: PT (INR)

*6 Tumor markers: AFP, AFP-L3 fraction, PIVKA-II

9. DATA COLLECTION

9.1. Types of Case Report Form (CRF) and Submission Deadlines

The types of case report forms used in this study and their submission deadlines are as follows.

- 1) Enrollment Eligibility Form: Fax to data center at enrollment
- 2) Patient Characteristics Report: Fax to data center within 2 weeks before the start of the study
- 3) Progress Report (each cycle): Fax to data center within 1 week after eligibility to start next cycle is confirmed
- 4) SAE Report (Expedited Primary Report): Fax to **study coordinator** within 72 hours of SAE onset
- 5) SAE Report (Expedited Secondary Report): Fax to **study coordinator** within 7 days of learning of the event
- 6) Adverse Event Report (Normal Report): Fax to **study coordinator** within 15 days of learning of the event
- 7) Treatment Response Report: Fax to data center within 4 weeks after the end of the protocol treatment
- 8) Treatment Completion Report: Fax to data center within 4 weeks after the end of the protocol treatment
- 9) Follow-up Form: Fax to data center within 2 weeks after receiving a request*
- 10) Treatment Suspension Report: Fax to the study chair when considering discontinuation for a patient who does not clearly meet the specified criteria for discontinuation of the protocol treatment

*Will be requested every 4 months following the monitoring schedule of the data center after the end of the study treatment.

9.2. Submission of Imaging Data

When submitting imaging data (CT or MRI) for interim analysis, each study site will mask personal information (e.g., ID number, name, date of birth) on data from enrollment and after discontinuation of the protocol treatment, write in the patient's enrollment number for this

study, and send the data to the study coordinator. DICOM data recorded on CD-R or DVD-R is generally preferred, but films are also acceptable. These should be submitted after discontinuation of the protocol treatment. Imaging data from enrollment will be collected for patients who did not start the protocol treatment.

9.3. Where to Direct Inquiries

- 1) Eligibility criteria, criteria for adjusting treatments, or imaging assessment, and inquiries requiring clinical judgment: Study Coordinator
- 2) Enrollment procedures or completion of CRFs: Data Center
- 3) Serious Adverse Event Reports: Study Chair/Study Coordinator

9.4. Data Management

Data sent to the data center will be anonymized in a linkable fashion at each study site. These data will be strictly managed in accordance with institutional standards. The data center will notify each participating institution of the serial numbers assigned to each enrolled patient. Data collected by the data center will be kept under strict control using these serial numbers.

When study results are presented at academic conferences or published in academic journals, measures will be taken to ensure study subjects cannot be identified. (See **Section 17. PUBLICATION OF STUDY RESULTS**). Patient data will be deleted if they withdraw their consent. However, results of analysis will not be deleted if study results have already been published.

If data from this study is used for secondary purposes, such as meta-analysis, personal information will be kept strictly confidential and measures will be taken to ensure study subjects cannot be identified.

10. REPORTING OF ADVERSE EVENTS

If a serious adverse event or unexpected adverse event occurs, the investigator will report the event to the study chair. Reports to institutional directors, drug safety reports for the Ministry of Health, Labour and Welfare, and unsolicited reports from medical institutions to the manufacturer through the manufacturer reporting system defined in the Pharmaceutical Affairs Law will be made as appropriate in accordance with institutional regulations and will be the responsibility of individual investigators.

10.1. Adverse Events Subject to Mandatory Reporting

10.1.1. Adverse Events Subject to Expedited Reporting

Adverse events that meet any of the below criteria are subject to expedited reporting.

1) All deaths that occur during the protocol treatment or within 30 days* of the last day of the protocol treatment

This applies regardless of causality. In the case of patients who discontinued the protocol treatment, all deaths within 30 days of the last day of the protocol treatment are subject to expedited reporting, even if the patient already started post-trial treatment.

*: Here, “30 days” refers to 30 days beginning from the day after the last day of the protocol treatment, with the last day of treatment considered as day 0.

** : Deaths of patients who did not receive the protocol treatment after enrollment are not subject to expedited reporting. However, evaluation of eligibility at enrollment and other necessary evaluations will be made as appropriate through regular monitoring.

2) Unexpected grade 4 adverse events

Grade 4 adverse events that are not listed on the package inserts for the study drugs and are judged to have a causal relationship (definite, probable, or possible) with the protocol treatment are subject to expedited reporting.

10.1.2. Adverse events subject to regular reporting

Adverse events that meet any of the criteria in 1) through 4) below and are judged to have a causal relationship (definite, probable, or possible) with the protocol treatment are subject to regular reporting.

1) Deaths that occur 31 days or more after the last day of the protocol treatment

This applies to deaths suspected to be treatment-related. It does not apply to deaths clearly caused by the primary disease.

2) Expected grade 4 non-hematological toxicity (adverse event not in the blood/bone marrow categories in CTCAE v4.0)

Grade 4 non-hematological toxicity listed in the package inserts for the study drugs. Note that serious adverse events are subject to regular reporting even if expected.

3) Unexpected grade 2 and grade 3 adverse events

Grade 2 or 3 adverse events not listed in the package inserts for the study drugs.

4) Other clinically significant medical events

10.2. Reporting Obligations of Investigators and Reporting Procedures

10.2.1. Expedited reporting

If an adverse event subject to expedited reporting occurs, the investigator will promptly notify the lead site investigator and the medical representative of the manufacturer. If the lead

site investigator cannot be reached, the site coordinator or the investigator must perform this duty in place of the lead site investigator.

Primary reporting

Within 72 hours of learning of the adverse event, the lead site investigator will complete the designated items on the SAE Report (Expedited Primary Report), fax the report to the study coordinator, and notify the study coordinator by phone. They will also contact the medical representative of the manufacturer by phone or another appropriate means.

Secondary reporting

Investigators will prepare an SAE Report (Expedited Secondary Report) (appended) and a separate Case Details Report (appended) with more detailed information and mail or fax the report to the study chair within 7 days of learning of the event. As prompt submission is of the highest priority, it is acceptable if some items on the report cannot be completed due to uncertainty.

Additional reporting

Investigators will prepare an Adverse Event Report (Additional Report) (appended) only if there were issues with the secondary report.

10.2.2. Regular reporting

Within 15 days of learning of the adverse event, the lead site investigator will complete the designated items on the Adverse Event Report (Regular Report) (appended), and mail or fax the report to the study coordinator.

10.3. Responsibilities of the Study Chair/Study Coordinator

Upon receiving a report from the lead site investigator, the study coordinator will report this to the study chair and research group representatives and consult with them about the report. The urgency, importance, and impact of the report contents will be determined, and measures such as temporary suspension of enrollment (the data center and all participating institutions would be contacted) or urgent notification of participating institutions to inform them of the matter will be taken if necessary. The data center and participating institutions may be contacted by phone if the matter is very urgent, but the phone call should be promptly followed by written correspondence (sent by fax, mail, email, or in person).

10.4. Evaluation by the Data and Safety Monitoring Committee

If an adverse event reported by a participating institution by expedited reporting or regular reporting is judged to meet the criteria in **10.1. Adverse Events Subject to Phase III Trial Comparing Sorafenib Monotherapy with Low-dose FP + Sorafenib Combination Therapy** / Page 52 of 89

Mandatory Reporting after the study coordinator consults with the study chair about the event, the study coordinator will consult with the research group representative and send a written report of the event to the Data and Safety Monitoring Committee office within 15 days of learning of the event. At the same time, they will request that the committee review the opinion of the study chair regarding the adverse event and the appropriateness of measures to be taken.

When they do so, they will include information such as the results of evaluation by the study coordinator/study chair and measures to be taken (including the decision on whether to continue or suspend the study) on SAE Reports (Expedited Primary Reports) and Adverse Event Reports (Regular Reports) sent by participating institutions. In the event of a death within 30 days (**Section 10.1.1-1**), a death after 31 days or later judged to be treatment-related (**Section 10.1.2-1**), or an expected grade 4 non-hematological toxicity (**Section 10.1.2-2**), these notes will include not only the course of individual patients, but also discussion regarding whether the incidence was within the expected range. If the observed incidence is determined to be outside the expected range, this fact will be also be recorded on the Adverse Event Report.

11. ANALYSIS AND ENDPOINT DEFINITIONS

11.1. Analysis

The additive effect of low-dose FP on sorafenib monotherapy will be evaluated by overall survival (OS). The distribution of time to death in each group will be calculated using the Kaplan-Meier method. The Cox proportional hazards model will be used to evaluate efficacy. Interim analysis will not be performed in this study.

Analysis by average sorafenib dose will also be performed as a subgroup analysis. Infusion frequency and overall survival will also be compared in the HAIC group. Overall survival will also be compared by baseline patient characteristics (hepatic function, age, sex, and tumor markers).

11.2. Imaging Interpretation

Interpretation of imaging results at two points, enrollment and discontinuation or completion of the protocol treatment, will be performed by central review by the **Central Imaging Interpretation Committee (Section 16.7.)**.

10.3. Definitions of Analysis Populations

The analysis populations for regular monitoring and final analysis are defined as follows.

All enrolled patients

The “all enrolled patients” population consists of all patients enrolled in accordance with **Section 5.1. Enrollment and Randomization Procedures** excluding duplicate enrollments and erroneous enrollments.

Ineligible patients

The “ineligible patients” population consists of enrolled patients who did not meet the eligibility criteria (ineligibility was discovered at a later date) or were unable to start the protocol treatment.

All eligible patients

The “all eligible patients” population consists of all enrolled patients except patients determined to be ineligible by the research group. Patients judged to be ineligible at the sole discretion of an investigator, site coordinator, or lead site investigator are included in “all eligible patients”. In order for the research group to judge a patient ineligible, the chair of the research group must approve the designation during the final analysis. For analysis for regular monitoring or when presenting data at an academic conference before submission of the final analysis report, the data center may choose to not include patients judged to be ineligible by the study coordinator with the understanding of the study coordinator.

Full analysis set

The full analysis set consists of all enrolled patients who completed the protocol treatment in whole or in part. Patients who did not start the protocol treatment at all are considered “untreated patients”.

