6. TREATMENT PLANS AND CRITERIA FOR ADJUSTING TREATMENT

6.1. Protocol Treatments

6.1.1. Low-dose FP and sorafenib group (combination therapy group) (Table 1)

This study will use the following doses demonstrated as safe in a phase I/II study of sorafenib and low-dose cisplatin/fluorouracil hepatic arterial infusion chemotherapy for advanced hepatocellular carcinoma. Cisplatin will be administered at a dose of 20 mg/m² on day 1 (within 30 days), and fluorouracil will be administered at a dose of 330 mg/m²/day by hepatic infusion using a reservoir for 5 days from day 1 through day 5 (continuous infusion over 24 h), followed by 2 days off. This sequence will be repeated for 2 weeks, followed by 2 weeks off. Sorafenib will be administered continuously at a dose of 400 mg twice daily for 28 days from day 1 to day 28. This 4-week period constitutes one cycle.

The first cycle of treatment will be started within 28 days of randomization. Treatment with sorafenib before hepatic arterial infusion chemotherapy will be allowed. However, patients must be off sorafenib for 2 days before and 7 days after reservoir placement. The next cycle of treatment will be started within 14 days. Sorafenib will be continued until the start of the next cycle. This combination therapy will be continued until discontinuation of the protocol treatment.

If an adverse event is observed, treatment will be interrupted or the dose will be reduced as appropriate in accordance with **6.3.2. Criteria for adjusting the sorafenib dose (dose interruption and reduction)** and **Section 6.3.3. Criteria for Hepatic Arterial Infusion Chemotherapy (Low-dose FP) Dose Adjustment (Dose Interruption and Reduction)**. After the protocol treatment is discontinued, appropriate treatment as described in **Section 6.5 Post-trial Treatment** will be instituted.

The arterial catheter should be placed in a manner that allows for proper drug distribution throughout the liver, and the flow should always be checked by contrast CT through the port or by DSA before starting treatment.

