11.4. Patients Included in Analysis

Analysis populations

Safety evaluation: Randomized patients will be included in the safety evaluation.

Efficacy evaluation: The full analysis set (FAS) defined in Section 11.3 will be used.

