11.6. Endpoint Definitions

11.6.1. Primary endpoint

Overall survival (OS)

The length of time from the date of randomization until death from any cause. The date survival was last confirmed will be used to censor surviving patients. Unfollowable patients will be censored by the date survival was last confirmed before they became unfollowable.

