12.2. Enrollment Period and Follow-up Period

Enrollment period: **45 months**, Follow-up period: 12 months

Initially, the study was started in October 2010 with a planned enrollment period of 24 months. However, the actual pace of enrollment was slower than expected, so the enrollment period was extended by one year in January 2012. As of August 2013, 180 patients (94.7%) have enrolled. Many patients have been unable to start the protocol treatment. Therefore, upon consultation with the research group, it was decided to extend the enrollment period, which was to conclude at the end of September 2013, by 9 months to the end of June 2014.

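### The primary survival analysis leaves out every randomised patient who never started treatment, so it is not intention-to-treat and is open to selection bias of unknown size and direction

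*Protocol*

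**What the plan says.** Section 11.4 names one population for efficacy: "Efficacy evaluation: The full analysis set (FAS) defined in Section 11.3 will be used". The section it points to is printed as 10.3 and reads: "The full analysis set consists of all enrolled patients who completed the protocol treatment in whole or in part". The next sentence sets the remainder apart: "Patients who did not start the protocol treatment at all are considered" untreated. The same section also places patients who could not start among the ineligible.

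The OS clock in Section 11.6.1 starts earlier: "The length of time from the date of randomization until death from any cause". Between the two lies a window, stated for both arms in Sections 6.1.1 and 6.1.2: "The first cycle of treatment will be started within 28 days of randomization".

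Safety gets the wider population: "Safety evaluation: Randomized patients will be included in the safety evaluation".

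Section 12.2, explaining the second extension of enrollment, reports: "Many patients have been unable to start the protocol treatment". It gives no number and no split by arm.

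No efficacy analysis of all randomised patients is named. Section 14.2 monitors OS in eligible patients, a set that can also lose those who could not start.

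**The concern.** Whether a patient starts treatment is decided after randomisation, and in an open-label trial it is decided by people who know the assignment (Section 5.2 has the site informed at enrollment). A patient who deteriorates, dies or declines before the first dose is an OS observation by Section 11.6.1 but is absent from the OS comparison. If the two arms lose different numbers or kinds of patients this way, the groups compared are no longer the groups randomised, and neither the hazard ratio nor the one-sided 0.05 error rate is protected.

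The routes out differ by arm. Only the combination needs a reservoir, and Section 7.2 anticipates catheterisation complications before treatment begins. The control arm has no such step, but its patients know they did not receive the experimental treatment and may decline to start. What is at stake is the trial's single confirmatory result.

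**Working it through.** **1. Who is counted.** Applying the text to three possible patients:

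| Patient | OS observation under 11.6.1 | In the efficacy set |
|---|---|---|
| Combination, dies before any drug | Yes | No |
| Combination, takes sorafenib while awaiting the reservoir, never infused | Yes | Yes (treated in part) |
| Monotherapy, learns the assignment and declines to start | Yes | No |

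The set is therefore conditional on events after randomisation. This step needs no assumption.

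**2. How many.** The plan's own figure reproduces: 180/190 = 94.7% enrolled by August 2013. The untreated number cannot be derived, so the shares below are assumed.

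**3. Effect on the test when the treatments do not differ (true hazard ratio 1).** Inputs from Section 12.1: 95 per arm, control median 10 months (hazard ln 2/10 = 0.0693 per month), 24 months of enrollment plus 12 of follow-up, one-sided 0.05. Assumed: both arms contain the same fraction of poor-prognosis patients, equal to the larger untreated share, with hazard k times the rest, and the untreated come from that fraction. The test is the log-rank score test (Section 11.1 names the Cox model). The hazard ratio is exp[mean of (O-E)/V], and the null is rejected when -(O-E)/√V > 1.645. There were 4,000 trials per scenario, so the Monte Carlo standard error at 5% is √(0.05×0.95/4000) = 0.34 percentage points.

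| Untreated, combination / monotherapy | k | Hazard ratio, treated only | One-sided error, treated only |
|---|---|---|---|
| 5% / 5% | 2 to 5 | 1.00 | 5% |
| any pair above or below | 1 | 1.00 | 5% |
| 10% / 5% | 2 to 5 | 0.98-0.94 | 6-9% |
| 10% / 2% | 2 to 5 | 0.95-0.92 | 9-13% |
| 15% / 2% | 2 to 5 | 0.92-0.87 | 12-20% |
| 2% / 10% | 2 to 5 | 1.05-1.09 | 3-1.5% |

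Analysing all randomised patients gave hazard ratios of 1.00 and errors of 4.5-5.9% throughout.

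These selections are strong. At 10%/2% the combination arm loses all its poor-prognosis patients, while monotherapy keeps 8 of every 98 analysed (8.2%). A second model is less extreme: 25% poor-prognosis patients in each arm at 2 to 3 times the hazard, 45 plus 12 months, 3,000 trials.

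- 15%/3%, all untreated from the poor group: hazard ratio 0.94-0.92, error 10-13%.
- 15%/3%, half of the untreated unrelated to prognosis: 0.97-0.96 and 7-9%.
- 15%/3%, untreated unrelated to prognosis: 1.00 and 4-5%.
- 10%/7%, all from the poor group: 0.99-0.98 and about 6%.
- 3%/15%, all from the poor group: 1.07-1.09 and 1-2%.

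**4. Whether power stands in the way of the change.** Required events are d = 4(z_α+z_β)²/(ln HR)². With HR = 1/1.7, (ln HR)² = 0.2816. Two-sided 0.05 gives 4×7.849/0.2816 = 111.5, so 112, the plan's figure. The stated one-sided 0.05 gives 4×6.183/0.2816 = 87.8, so 88. That mismatch is a separate matter. The event probability is 1-[e^(-λF)-e^(-λ(A+F))]/(λA) with A = 24 and F = 12: 0.788 at median 10, 0.609 at median 17, mean 0.698. All 190 patients give 132.7 events and power Φ(√(132.7/4)×0.5306-1.645) = 92% one-sided (86% at two-sided 0.05). With about 15% lost or excluded, 161 patients give 112.4 events and 88% (80%). These powers assume the planned hazard ratio across everyone analysed. Untreated combination patients would dilute it, so 92% is an upper figure.

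**The case against.** A reader might infer that the analysis is biased towards the combination arm. The documents do not support that firmly. They give no untreated counts, reasons or prognoses by arm. The reservoir is also a weaker hurdle than it looks. Sections 0.5.1 and 6.1.1 allow sorafenib before infusion, and a patient who has taken any counts as treated in part. The two-day hold before placement can apply only to someone already on sorafenib, who is therefore already in the set. The reservoir removes a patient only if no sorafenib was taken either. Control patients who decline once they know their assignment would push the other way. This objection stands in full against a claim about direction.

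A second objection is that untreated patients say nothing about the drugs, and that leaving out those with no dose can be harmless. It can be, where knowledge of the assignment cannot influence who starts. Here assignment is open and the pre-treatment steps differ by arm, so that condition is not met.

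A third is that a statistical analysis plan may add an all-randomised analysis. The protocol does not leave the point open: it names the efficacy population, and a different one elsewhere would contradict it.

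**Conclusion.** The structural point holds on the text alone. The primary OS comparison excludes all randomised patients who never started, so it is not intention-to-treat, and Section 12.2 shows that the excluded group is not negligible.

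Bias towards the combination is plausible but not established. The size ranges from nothing (equal shares, or untreated patients of average prognosis) to a hazard ratio of 0.87 with a 20% error rate (15% versus 2%, hazard five times the rest), and passes through 1 to 1.09 with 1.5% if the shares are reversed. Every untreated share and hazard multiple is an assumption. The case for change does not depend on direction: a confirmatory superiority claim should not rest on a set whose bias cannot be bounded from the plan when the unbiased set is available.

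**What to change.** - **Primary set (11.3/11.4).** Use all randomised patients, analysed as assigned, excluding only duplicate enrollments. The existing set of all enrolled patients serves once its undefined exclusion of erroneous enrollments is removed.
- **Sensitivity.** Keep the treated-only set under a name that says so.
- **Eligibility.** Stop classing patients who could not start as ineligible; failing to start is an outcome after randomisation.
- **Safety.** Base it on treated patients, and state whether reservoir placement counts as the start of treatment, so that catheterisation events before the first drug dose are not lost.
- **Reporting.** Give the untreated by arm, with reasons.
- **Follow-up (8.4/9.1).** Extend survival follow-up to untreated patients. As written it begins when treatment is discontinued, and follow-up forms are requested after treatment ends, so registration at the data center alone will not supply their survival status.
- **Section number.** Correct the printed 10.3 to 11.3.

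The cost is protocol wording, a small amount of extra survival follow-up, and a possibly less favourable estimate. No additional patients are needed.
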